#### **9.2.4 Medical History**

Data will be collected from patients at baseline consisting of medical history, including previous cardiac investigations, previous cardiac history, and medications taken in the past month.

#### **9.2.5 Clinical Assessment**

A routine clinical assessment is required at baseline, and at all in-person visits. Any abnormality must be recorded.

#### **9.2.6 Vital Signs, Body Height and Weight**

Vital signs including blood pressure, HR and body weight will be recorded at baseline (Visit 1), and at all in-person visits. Body height will be recorded at baseline (Visit 1).

#### **9.2.7 Collection of NRS Scores**

Patients will be asked to enter their pain scores into a diary on a daily basis using the 11-point NRS. Patients will have the choice to complete the NRS scale either on paper or in an electronic patient reported outcomes platform – i.e., eSOC DAT Patient Portal. Access to the eSOC DAT Patient Portal is restricted to authorized users only. State-of-the-art procedures are in place to prevent unauthorized access and data corruption, namely, firewalls, up-to-date virus scanning in addition to the encryption of data stored in the database and transmitted via the Internet. Patients will be provided with a unique username and password to access the eSOC DAT Portal.

In addition, the highest NRS pain score within the past 7 days will be recorded at baseline (patient recall) and at each visit after randomization from the Patient Portal entries/diaries or, if not available, from patient recall.

#### **9.2.8 Concomitant Treatment**

Guidelines for concomitant treatment are given in Section 6.6 of this protocol.

All changes in concomitant medications during the study must be recorded, as must those started within one week of study entry and continued thereafter.

### **9.2.9     Laboratory Tests**

Laboratory tests include CRP, CBC, AST/ALT, alkaline phosphatase, bilirubin, creatinine/eGFR, INR, pregnancy test (female patients of childbearing potential only). Please see Appendix 17.2 for the exact schedule of all laboratory tests. Visit 4 (Week 3) can only be virtual if the laboratory assessments can be performed by a local laboratory.

### **9.2.10    C-SSRS**

The C-SSRS is a questionnaire designed for the assessment of suicidal ideation and behavior in adolescents and adults.

To monitor for the emergence of suicidal ideation and behavior, patients will undergo C-SSRS evaluations at baseline, at Week 8 and at Week 26.

The questionnaire must be administered by an investigator or other individual that is suitably qualified by education or training. See Appendix 17.4 for a sample C-SSRS - Baseline/Screening version assessment and Appendix 17.5 for a sample post-dose C-SSRS assessment.

If a patient becomes suicidal during the study, an investigator or medically qualified sub-investigator should provide the appropriate treatment to the patient.

### **9.2.11    Management of AEs**

#### ***9.2.11.1   AE Reporting***

An AE is defined as any new untoward medical occurrence or worsening of a pre-existing medical condition in a patient or clinical investigation patient administered an investigational (medicinal) product and that does not necessarily have a causal relationship with this treatment. An AE can therefore be any unfavorable and unintended sign (including an abnormal laboratory finding, for example), symptom, or disease temporally associated with the use of investigational product, whether or not considered related to the investigational product.

AEs can be spontaneously reported or elicited during open-ended questioning, examination, or evaluation of a patient. (In order to prevent reporting bias, patients should not be questioned regarding the specific occurrence of one or more AEs.)

Any AE that results in any of the following outcomes will be considered an SAE:

1. Death

2. Life-threatening situation (patient was at risk of death at the time of the event. This does not refer to an event that might have caused death if it was of greater intensity.)
3. New in-patient hospitalization or prolongation of existing index hospitalization
4. Persistent or significant disability or incapacity
5. Congenital anomaly or birth defect
6. QTc interval increases to > 500 msec or >60 msec from baseline.
7. Important medical events that may not result in death, be life-threatening, or require hospitalization but may jeopardize the patient and may require medical or surgical intervention to prevent one of the above outcomes (based upon appropriate medical judgment), e.g., allergic bronchospasm requiring intensive treatment in an emergency room or at home, blood dyscrasias or convulsions that do not result in in-patient hospitalization, or the development of drug dependency or drug abuse. Potential Drug-Induced Liver Injury (DILI) is also considered an important medical event. (See Section 9.2.11.3 for the definition of potential DILI.)

All SAEs experienced by a patient after informed consent has been obtained must be reported to SOCAR Research (SOCAR) within 24 hours of the site's awareness of the event.

The term “severe” is often used to describe the intensity (severity) of a specific event (as in mild, moderate, or severe pain); the event itself, however, may be of relatively minor medical significance (such as severe headache). By contrast, the term “serious” is used to describe an event based on an event outcome or actions usually associated with events that pose a threat to a patient’s life or functioning. Seriousness (not severity) serves as a guide for defining regulatory reporting obligations.

For all collected SAEs, the clinician who examines and evaluates the patient will determine the event’s causality based on temporal relationship and his/her clinical judgment. The degree of certainty about causality will be graded using the categories below:

**Definitely Related:** There is clear evidence to suggest a causal relationship, and other possible contributing factors can be ruled out.

**Probably Related:** There is evidence to suggest a causal relationship, and the influence of other factors is unlikely.

**Possibly Related:** There is some evidence to suggest a causal relationship. However, the influence of other factors may have contributed to the event.

**Unlikely:** A clinical event, including an abnormal laboratory test result, whose temporal relationship to drug administration makes a causal relationship improbable and in which other drugs or chemicals or underlying disease provides plausible explanations.

**Not Related:** The SAE is *completely independent of study drug administration, and/or evidence exists that the event is definitely related to another etiology.*

Pre-existing conditions should be recorded upon patient enrolment (including start date of the condition, and severity - mild, moderate, severe). After the patient signs the informed consent form, any worsening of these conditions would be recorded.

Any new conditions would be recorded including date of onset, date of resolution, severity (mild, moderate, severe, or serious as defined above) and possible relationship to study drug or procedure. As part of the source notes, follow up clinical assessments, laboratory tests, ECGs and diagnostic imaging related to AE should be documented.

#### **9.2.11.2 *Pregnancy***

If, following initiation of the investigational product, it is subsequently discovered that a study patient is pregnant or may have been pregnant at the time of investigational product exposure, including during at least 6 half-lives after product administration, the investigational product will be permanently discontinued, and the pregnancy will be reported to SOCAR within 24 hours of the site's awareness of the event.

Protocol-required procedures for study discontinuation and follow-up must be performed on the patient unless contraindicated by pregnancy. Other appropriate pregnancy follow-up procedures should be considered if indicated.

#### **9.2.11.3 *Drug-Induced Liver Injury (DILI)***

Wherever possible, timely confirmation of initial liver-related laboratory abnormalities should occur prior to the reporting of a potential DILI event. All occurrences of potential DILIs, meeting the defined criteria below, must be reported as SAEs.

Potential DILI is defined as:

1. ALT or AST elevation  $> 8 \times \text{ULN}$ 

OR
2. ALT or AST elevation  $> 5 \times \text{ULN}$  for more than 2 weeks

OR
3. ALT or AST elevation  $> 3 \times \text{ULN}$  and bilirubin  $> 2 \times \text{ULN}$  or INR  $> 1.5$ .

If a patient meets one of the above criteria, the study drug needs to be discontinued and the investigator is to arrange for the patient to return to the investigational site as soon as possible (within 24 hours of notice of abnormal results) for repeat assessment of ALT, AST, bilirubin and alkaline phosphatase, detailed history, and clinical assessment. Patients are to be followed in this way until all abnormalities have normalized (in the

investigator's opinion) or returned to the baseline state. If the patient cannot return to the investigational site, repeat assessments could be performed at a local laboratory (and the results are then to be sent to SOCAR by the investigator).

Elevations in ALT or AST  $> 3 \times$  ULN or bilirubin  $> 2 \times$  ULN alone, i.e., when not concomitant, are not grounds for withdrawal but are to be followed up, as above, within 72 hours of notice of abnormal results.

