#### 4.2.2 Safety Parameters

Safety parameters include the number of AEs and SAEs, changes in C-SSRS as well as changes in laboratory parameters, including liver function parameters and INR as well as ECG intervals and rhythm during the 26-week study period.

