- Study drug dose increase to 10 mg/kg of body weight b.i.d. if patient tolerating 7.5 mg/kg of body weight b.i.d. If patient did not tolerate 7.5 mg/kg of body weight b.i.d., patient can return to 5 mg/kg of body weight b.i.d.
- Study drug accountability
- Recording of changes in concomitant medications
- AE and SAE recording

Visit 4 (Week 3 ± 3 days) – This visit may be performed as a virtual visit if an in-person visit is not possible as long as the ECG recording can be obtained and the laboratory assessments can be done by a local laboratory.

The following evaluations will be performed at 2 weeks after start of study medication:

- Clinical assessment (if visit in person)
- Vital signs, including HR and blood pressure (if visit in person)
- Review/collection of daily diary NRS pain scores, if not submitted electronically to Patient Portal if the patient has completed the questionnaire on paper

- Collect highest NRS pain score within the past 7 days
- 12-lead ECG 5 hours post morning dose (time window 3.5 – 6 hours); QTc intervals on ECG to be reviewed by site investigator, or designate, who decides if patient can continue study medication. If the visit is done remotely, the patient will record the ECG on a portable device at home or will have the ECG recording performed at a local clinic. The tracings must immediately be transmitted to the site for review.
- Study drug dose adjustment (if patient did not tolerate 10 mg/kg of body weight b.i.d., patient can return to 7.5 mg/kg of body weight b.i.d.)
- Study drug accountability
- Recording of changes in concomitant medications
- AE and SAE recording
- Local laboratory assessments, including CRP, CBC, AST/ALT, alkaline phosphatase, bilirubin, creatinine/eGFR, INR (if visit not in person, patient needs to go to a local laboratory for blood collection and assessments)

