#### Visit 5 (Week 8 ± 4 days) – final study visits for patients not continuing in the EP

The following evaluations will be performed at 8 weeks after start of study medication:

- Clinical assessment
- Vital signs, including HR, blood pressure and body weight
- Review/collection of daily diary NRS pain scores, if not submitted electronically to Patient Portal if the patient has completed the questionnaire on paper
- Collect highest NRS pain score within the past 7 days
- 12-lead ECG 5 hours post morning dose (time window 3.5 – 6 hours); QTc intervals on ECG to be reviewed by site investigator, or designate, who decides if patient can continue study medication
- C-SSRS
- Study drug accountability
- Recording of changes in concomitant medications
- Start weaning background therapy over the next 8 weeks for patients continuing in the EP
- AE and SAE recording
- Local laboratory assessments, including CRP, CBC, AST/ALT, alkaline phosphatase, bilirubin, creatinine/eGFR, INR

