#### Visit 6 (Week 12 ± 4 days) – Virtual visit

The following evaluations will be performed virtually at 12 weeks after start of study medication:

- Review/collection of daily diary NRS pain scores, if not submitted electronically to Patient Portal
- Collect highest NRS pain score within the past 7 days
- Study drug accountability
- Recording of changes in concomitant medications
- AE and SAE recording

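### The liver follow-up in Protocol 9.2.11.3 omits INR, although INR above 1.5 is a stop trigger for patients kept on drug with isolated ALT/AST above 3x ULN

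*Protocol*

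**What the plan says.** Protocol Section 9.2.11.3 defines potential drug-induced liver injury by three criteria:

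- ALT or AST above 8x ULN;
- ALT or AST above 5x ULN for more than 2 weeks;
- ALT or AST above 3x ULN and bilirubin above 2x ULN or INR above 1.5.

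Meeting any one of them requires study drug to be stopped, and Section 6.5.1 makes that stop permanent. The patient is to return within 24 hours "for repeat assessment of ALT, AST, bilirubin and alkaline phosphatase, detailed history, and clinical assessment". The section continues: "Patients are to be followed in this way until all abnormalities have normalized", in the investigator's opinion, or are back at the baseline state.

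Patients with only ALT/AST above 3x ULN, or only bilirubin above 2x ULN, stay on drug. Those elevations "alone, i.e., when not concomitant, are not grounds for withdrawal but are to be followed up, as above, within 72 hours" of notice.

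INR is in the routine set in Section 9.2.9: "Laboratory tests include CRP, CBC, AST/ALT, alkaline phosphatase, bilirubin, creatinine/eGFR, INR, pregnancy test". It is also a declared safety parameter in Section 4.2.2: "changes in laboratory parameters, including liver function parameters and INR as well as ECG intervals and rhythm during the 26-week study period".

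**The concern.** Follow-up of an isolated transaminase elevation in a patient who is still dosing exists to find out whether the elevation is turning into something that requires a stop. One way of reaching the stop is an INR above 1.5, and the named repeat tests do not measure it. Section 14.4.1 asks sites to follow the protocol exactly, and 9.2.11.3 allows the repeat to be done at a local laboratory when the patient cannot return. An order copied from the list would leave INR out. The stake is that a patient could keep taking a drug that the protocol's own rule says must be stopped.

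The group can exist from the first dose. Exclusion criterion 3 admits ALT/AST between 3x and 5x ULN provided bilirubin is not above 2x ULN.

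**Working it through.** **1. Stop criteria against the repeat list (both in 9.2.11.3)**

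| Analyte | Used in a stop criterion | In the repeat list |
|---|---|---|
| ALT, AST | yes (1, 2 and 3) | yes |
| Bilirubin | yes (3) | yes |
| INR | yes (3) | **no** |
| Alkaline phosphatase | no | yes |

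INR is the only trigger analyte missing.

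**2. Is INR supplied elsewhere?** Section 9.1 lists INR at baseline and at Weeks 3, 8, 16 and 26. Section 9.2.9 refers to that schedule. Appendix 17.8 asks for INR monitoring in warfarin users. SAP Section 8.6.4 summarises INR but adds no draw. Apart from the warfarin advice, nothing puts INR into the unscheduled liver repeat.

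**3. How criterion 3 parses.** The line has no brackets.

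- Reading A: ALT/AST above 3x ULN, with either bilirubin above 2x ULN or INR above 1.5.
- Reading B: ALT/AST above 3x ULN with bilirubin above 2x ULN; or INR above 1.5 by itself.

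INR is a stop trigger under both. The rest uses reading A, which gives the narrower gap.

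**4. When the omission changes the decision (reading A).** The patient is on drug after an isolated ALT/AST elevation, and all of these hold:

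- ALT/AST still above 3x ULN, but not above 8x and not above 5x for more than 2 weeks;
- bilirubin at or below 2x ULN;
- INR normal at first, later above 1.5.

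If ALT/AST or bilirubin crosses its own limit, the listed repeat shows it. If ALT/AST falls to 3x ULN or below, the INR arm no longer applies.

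**5. Time to the next INR named in the protocol.** There are 8 post-baseline visits (Visits 2 to 9). INR is drawn at 4 of them (Visits 4, 5, 7 and 9). Day 3, Day 10 and the virtual visits at Weeks 12 and 20 have no laboratory tests.

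Nominal gap = 7 x (later week - earlier week). Range = nominal gap ± (sum of the two visit windows). The windows are those in Section 9.1: "Visit 4 (Week 3 ± 3 days", "Visit 5 (Week 8 ± 4 days", then ±4 days at Week 16 and ±5 days at Week 26.

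| Elevation found at | Next named INR | Nominal gap | Windows | Range |
|---|---|---|---|---|
| Week 3 | Week 8 | 7 x 5 = 35 days | 3 + 4 = 7 | 28-42 days |
| Week 8 | Week 16 | 7 x 8 = 56 days | 4 + 4 = 8 | 48-64 days |
| Week 16 | Week 26 | 7 x 10 = 70 days | 4 + 5 = 9 | 61-79 days |

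The last two rows concern extension patients only. Each gap is the longest that a rise could go without a named INR, since the rise may begin at any time within it.

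**The case against.** The case on the other side is substantial.

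- **The first INR is usually known.** At a scheduled draw, INR comes with ALT and AST. This stands. The gap is only a later rise.
- **The rest of the stop rule is checked.** ALT, AST and bilirubin are repeated, with a history and clinical assessment. Section 6.5.1 requires a stop for any condition that the investigator judges to need one. This stands and makes the case narrow.
- **Nothing forbids adding INR.** True, but a stop trigger should not depend on someone thinking to add it.
- **The text already requires follow-up to normalization and timely confirmation of initial liver abnormalities.** This covers an INR that was abnormal at the start. It does not reach a patient whose first INR was normal.

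A reader might also infer more than the documents support:

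- **Patients stopped on INR would never be re-tested.** Normalization of an INR cannot be established without measuring it, so a re-test is implied. Naming it there is clarification only.
- **Isolated bilirubin elevations carry the same gap.** On reading A they largely do not. If ALT/AST passes 3x ULN while bilirubin is still above 2x ULN, the bilirubin arm stops the drug, and both analytes are in the repeat.
- **An INR at the 72-hour repeat would bring detection forward by the visit gap less 3 days.** That is only the time to one extra INR, about 3 days after one already taken at the detecting visit. It would miss any later rise. What matters is INR at the serial repeats, whose interval is not stated, so the gain in detection time cannot be calculated.

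**Conclusion.** The point holds for patients kept on drug with isolated ALT/AST above 3x ULN. Followed as written, the repeat tests leave one mandatory stop trigger unmeasured between scheduled draws. It is minor: the case needs the specific combination in step 4 of the working, and the other arms of the rule are checked.

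The conclusion assumes that sites run the list as printed, that the elevation is found at a scheduled draw with a normal INR, and that the patient is not on warfarin under the Appendix 17.8 advice. The documents give no basis for estimating how many patients would be affected. No endpoint or planned analysis is affected.

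**What to change.** In Section 9.2.11.3, extend the repeat tests to ALT, AST, bilirubin, alkaline phosphatase and INR. State that this set applies at each repeat, in both the 24-hour pathway (drug stopped) and the 72-hour pathway (drug continued). The existing cross-reference then carries it to the isolated elevations.

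The cost is a few words in one section and one extra analyte per repeat draw. INR is already in the routine local set, and the visit schedule and SAP need no change.

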#### **9.2.11.4 Overdose**

All occurrences of overdose must be reported as SAEs. An overdose is defined as the accidental or intentional administration of any dose of a product that is considered both excessive and medically important.

#### **9.2.11.5 Drug-Drug Interactions**

CardiolRx™ is known to be metabolized largely through the cytochrome P450 enzyme system in the liver. A number of the drugs commonly used in the management of heart failure and other CV or concomitant conditions are also capable of being inducers or inhibitors of these enzymes. The patients should specifically be monitored for (S)AEs that might reflect Drug-Drug Interactions (DDIs). See Section 6.3 of the IB for more detailed discussion.

Drugs that are known to prolong QTc intervals must not be started during the study (Appendix 17.6).

In addition, to aid investigators in screening concomitant medications for risk of DDIs, a table of medications that serve as substrate for certain enzyme isoforms inhibited by CardiolRx™ has been prepared (Appendix 17.8).

### **9.2.12 Drug Accountability**

Drug accountability will be performed at all visits after randomization and start of study medication, including virtual visits.

## 10 CRITERIA FOR EVALUATION OF STUDY RESULTS

### ***10.1 Criteria for Evaluation of Efficacy***

#### **10.1.1 Primary Efficacy Outcome**

The primary efficacy endpoint of this Pilot study is the change in patient-reported pericarditis pain using an 11-point NRS from baseline (highest score within the past seven days of Day 1) to Week 8 (highest score recorded within the past seven days).

#### **10.1.2 Additional Efficacy Parameters of Interest**

Additional efficacy parameters of interest are listed in Section 4.1.3.

### ***10.2 Criteria for Evaluation of Safety***

The safety parameters are listed in Section 4.2.2.

### ***10.3 Description of Patient Groups for Analyses***

#### **10.3.1 Population for Efficacy and Safety Analyses**

All patients who were enrolled and took at least one dose of study medication will be included in the safety analyses.

Patients who do not tolerate the initial dose of 5 mg/kg of body weight b.i.d. will stay in the study for safety evaluations but will be replaced for the assessment of efficacy.

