### **6.5.1 Permanent Suspension of Study Treatment**

Permanent suspension of study treatment must occur in the following cases:

- If, in the view of the investigator, the patient experiences a severe allergic reaction that cannot be explained by the administration of any other medication.
- Development of liver function abnormality, as described in Section 9.2.11.3.
- Development of an AE or any medical condition, which, in the opinion of the investigator, necessitates permanent suspension of study treatment.
- If the patient did not tolerate the starting dose of 5 mg/kg of body weight b.i.d.
- Withdrawal of consent.

Patients have the right to discontinue study treatment for any reason. However, unless they withdraw consent and are no longer willing to participate, they should be followed for the remainder of the trial and all AEs should be reported, regardless of whether or not the event occurs under the care of another physician or institution.

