#### ***Start of study medication in the evening of Day 1.***

#### Visit 2 (Day 3 + 2 days) – This visit may be performed as a virtual visit if an in-person visit is not possible as long as the ECG recording can be obtained

The following evaluations will be performed on Day 3 after start of study medication:

- Vital signs, including HR and blood pressure (if visit in person)
- Review/collection of daily diary NRS pain scores, if not submitted electronically to Patient Portal if the patient has completed the questionnaire on paper

- 12-lead ECG 5 hours post morning dose (time window 3.5 – 6 hours); QTc intervals on ECG to be reviewed by site investigator, or designate, who decides if patient can continue study medication. If the visit is done remotely, the patient will record the ECG on a portable device at home or will have the ECG recording performed at a local clinic. The tracings must immediately be transmitted to the site for review.
- Study drug dose increase to 7.5 mg/kg of body weight b.i.d. if patient tolerating starting dose of 5 mg/kg of body weight b.i.d. (If patient did not tolerate the starting dose of 5 mg/kg of body weight b.i.d., the patient will stop the study medication but will continue in the study and follow all assessments until Visit 5 to be included in the safety analyses)
- Study drug accountability
- Recording of changes in concomitant medications
- AE and SAE recording

Visit 3 (Day 10 ± 2 days) – This visit may be performed as a virtual visit if an in-person visit is not possible as long as the ECG recording can be obtained

The following evaluations will be performed on Day 10 after start of study medication:

- Vital signs, including HR and blood pressure (if visit in person)
- Review/collection of daily diary NRS pain scores, if not submitted electronically to Patient Portal if the patient has completed the questionnaire on paper
- Collect highest NRS pain score within the past 7 days
- 12-lead ECG 5 hours post morning dose (time window 3.5 – 6 hours); QTc intervals on ECG to be reviewed by site investigator, or designate, who decides if patient can continue study medication. If the visit is done remotely, the patient will record the ECG on a portable device at home or will have the ECG recording performed at a local clinic. The tracings must immediately be transmitted to the site for review.

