## 11 STATISTICAL METHODS

### 11.1 Sample Size Estimation

No formal sample size was calculated for this Pilot study. Approximately 25 patients will be included in this study. Patients who do not tolerate the initial dose of 5 mg/kg of body weight b.i.d. will stay in the study for safety evaluations but will be replaced for the assessment of efficacy.

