### 11.2 Outcome Analyses

Given the small sample size and the design of the study (no placebo comparison), no inferential statistical analyses are planned.

Depending on their distribution, continuous variables will be expressed as mean  $\pm$  standard deviation (SD) or as median (interquartile range [IQR]). Categorical variables will be expressed in counts with percentages.

For all continuous variables, including the NRS pain scores, the change from baseline will be presented as summary statistics.

For categorical variables, summary statistics will be calculated.

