5 ANALYSIS POPULATIONS

5.1 Full analysis set (FAS)

All patients who were enrolled and who started the IMP will be included in the Full Analysis set.

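### The protocol replaces patients who cannot tolerate the starting dose for efficacy, the SAP keeps every starter in the FAS, and SAP 8.5 names no set, so the primary mean NRS change has two possible denominators

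*Protocol*

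**What the plan says.** Protocol 10.3.1 is headed as covering both efficacy and safety, but the only population it defines is the safety one: "All patients who were enrolled and took at least one dose of study medication will be included in the safety analyses". It then says that patients who do not tolerate the initial 5 mg/kg b.i.d. dose "will stay in the study for safety evaluations but will be replaced for the assessment of efficacy". Section 11.1 repeats that rule beside the planned enrolment: "Approximately 25 patients will be included in this study".

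Under Visit 2 in protocol 9.1, such a patient is handled as follows: "the patient will stop the study medication but will continue in the study and follow all assessments until Visit 5". The stated purpose is inclusion in the safety analyses; efficacy is not mentioned. Protocol 6.5.1, which lists starting-dose intolerance among the reasons for permanent suspension, says of patients who stop treatment that "they should be followed for the remainder of the trial and all AEs should be reported".

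SAP 5.1 makes no exception for these patients: "All patients who were enrolled and who started the IMP will be included in the Full Analysis set". SAP 5.2 defines the safety set in the same way. SAP 8.3 names the FAS for baseline summaries and SAP 8.6 names the safety set for safety. SAP 8.5, 8.5.1 and 8.5.2 name no set for efficacy. SAP section 3 sends the reader to protocol 11.1, where the replacement rule stands.

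**The concern.** Whether a patient tolerates the first dose is known only after treatment has started. Choosing the efficacy set on that basis conditions it on a post-treatment outcome, and in a single-arm study no control group undergoes the same selection to offset it.

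The SAP neither adopts the protocol rule nor says that the FAS supersedes it. Two analysts following these documents could produce different primary tables, with different denominators and different means. The population should be settled early: SAP section 1 requires the SAP to be signed before the Week 8 analysis, and protocol 3.5 says that the results will inform a randomized withdrawal trial.

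**Working it through.** **The plan's own figure.** There is no calculation to reproduce. On sample size the protocol says "No formal sample size was calculated for this Pilot study", and on analysis "no inferential statistical analyses are planned". The check is a comparison of texts, followed by an illustration of size.

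**The texts side by side**

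| Question | Protocol | SAP |
|---|---|---|
| Are starting-dose-intolerant patients in safety? | Yes (10.3.1, 11.1, Visit 2) | Yes (5.2) |
| Are they in efficacy? | Replaced (10.3.1, 11.1) | In the FAS (5.1), but no set is named in 8.5 |
| Can they have a Week 8 NRS score? | Yes; they attend to Visit 5, where NRS is collected | Yes; 8.5.1 uses the daily diary and the eCRF item |

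**Inputs**
- Tolerant patients: 25, taken from the approximate enrolment in protocol 11.1 on the reading that each intolerant patient is replaced.
- k, the number of intolerant patients replaced: not given. Assumed 1 to 5.
- D, the mean NRS change in intolerant patients minus that in tolerant patients: not given. Assumed 2 to 4 points. It is positive when intolerant patients improve less.
- Every intolerant patient has an observed Week 8 score. SAP 9.2 plans no general imputation, so any patient without a score would drop out and reduce the effective k.

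**Formula.** Let m_T and m_I be the mean changes in the two groups.

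FAS mean = (25 × m_T + k × m_I) / (25 + k)

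FAS mean − tolerant-only mean = k/(25 + k) × (m_I − m_T) = k/(25 + k) × D

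| k | FAS n | Tolerant-only n | k/(25+k) | Shift, D = 2 | Shift, D = 4 |
|---|---|---|---|---|---|
| 0 | 25 | 25 | 0% | 0 | 0 |
| 1 | 26 | 25 | 3.8% | 0.08 | 0.15 |
| 2 | 27 | 25 | 7.4% | 0.15 | 0.30 |
| 3 | 28 | 25 | 10.7% | 0.21 | 0.43 |
| 4 | 29 | 25 | 13.8% | 0.28 | 0.55 |
| 5 | 30 | 25 | 16.7% | 0.33 | 0.67 |

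Example at k = 4: if tolerant patients fall 4 points and intolerant patients do not change, the tolerant-only mean is −4.0 and the FAS mean is −4 × 25/29 = −3.45.

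**How likely is k ≥ 1?** For an assumed intolerance rate p among 25 starters, the chance of at least one is 1 − (1 − p)^25: 40% at p = 2%, 72% at 5% and 93% at 10%.

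SAP section 4 says that 6 patients enrolled under Amendment 1, and SAP 4.3 gives their starting dose as 2.5 mg/kg b.i.d. A rule tied to an initial dose of 5 mg/kg does not literally fit them. If those 6 are among the 25, 19 remain, and 1 − (1 − p)^19 gives 32%, 62% and 86%.

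**The case against.** **Replaced is not excluded.** The protocol never says that these patients are removed. One of the two statements sits under sample size, where topping up enrolment is a natural meaning. On that meaning the protocol and the FAS agree. This stands as a caution, and a reader should not take exclusion as stated fact. But the contrast with safety in 10.3.1, and the safety-only purpose given at Visit 2, make exclusion the more natural reading.

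**The SAP points one way already.** Both sets in SAP section 5 have the same members, no tolerant-only set exists, and SAP 8.5 includes all data from scheduled visits. That makes the FAS the likely default. It does not settle the point: the sentence in 8.5 says which data are used rather than which patients, and SAP section 3 refers back to the replacement rule. Part of SAP section 7 is not in the public text and could not be checked, but 8.5 is visible.

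**The direction is not known.** A reader might infer that the protocol rule drops treatment failures and so must favour the drug. The documents do not support that. Not tolerating the first doses is a tolerability outcome. These patients enter in pain and on background therapy, and may improve without study drug. If they improve as much as the others, D is zero; if more, the sign reverses.

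**Nothing inferential is at stake.** This is correct. Denominators and summary statistics are affected, but no error rate is.

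**The follow-up wording may not conflict.** A reader might take 6.5.1 and Visit 2 as a flat contradiction that touches the primary endpoint. Visit 5 is the final visit for patients who do not enter the extension (protocol 6.3 and 9.1), and the extension is defined by continuing study treatment (6.2), so the two can be read together. Either way, the Week 8 endpoint is unaffected.

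**Conclusion.** The concern holds as a conflict between the documents that should be resolved. The protocol's replacement rule, most naturally read, selects the efficacy set on a post-treatment outcome. The SAP keeps all starters in the FAS and does not say which set its efficacy analyses use.

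The effect on the primary mean is probably modest: about 0.08 to 0.67 NRS points for k = 1 to 5 and D = 2 to 4, and none if every patient tolerates the starting dose. Both k and D are assumptions, as the documents give neither. Overstatement of benefit is conditional on intolerant patients improving less. The follow-up wording is a separate and secondary matter.

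**What to change.** 1. In SAP 8.5, state that the primary and all other efficacy analyses use the FAS, including starting-dose-intolerant patients with their observed Week 8 NRS.
2. In protocol 10.3.1 and 11.1, clarify that replacement means only that enrolment may be topped up.
3. Report the number replaced in the disposition summary (SAP 8.2), and show the tolerant-only set as a sensitivity summary of the primary endpoint.
4. State how the rule applies to the 6 Amendment 1 patients, who started at 2.5 mg/kg b.i.d.
5. Separately, reconcile the follow-up wording in protocol 6.5.1 with that under Visit 2 in 9.1.

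The cost is a SAP sentence, a protocol clarification and one extra summary. No new data are needed, because a Week 8 NRS is already scheduled for these patients. The downside is that the primary mean may look slightly less favourable.
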